#### MDASI-AML/MDS

The MDASI-AML/MDS is a validated modulized patient reported outcome measure for AML and MDS. It consists of a 19-item core cancer module and a 4-item AML/MDS specific module. The 23 items are designed to measure 13 core cancer symptoms (pain, fatigue, nausea, disturbed sleep, distress, shortness of breath, problem remembering, lack of appetite, drowsiness, dry mouth, sadness, vomiting, and numbness), 4 AML/MDS-specific symptoms (malaise, diarrhea, muscle weakness, and skin problems), and 6 areas of interference (general activity, mood, work, walking, relations with other people, and enjoyment of life).

Patients are asked to rate the severity of symptoms and related interference at their WORST level in the last 24 hours by responding to each item on an 0-10 numeric rating scale (NRS), where 0 = “not present” or “did not interfere” and 10 = “as bad as you can imagine” or “interfered completely”.

For this study, the response for the single item “Fatigue” (one of the 13 MDASI core cancer symptoms) will be analyzed separately as the key secondary efficacy endpoint.

Note that the electronic system capturing PRO data is set up in such a way that no questions on a questionnaire can be skipped. Hence, the questionnaires are either 100% or 0% completed.

### **EQ-5D-5L**

The EQ-5D-5L is a brief, self-administered, validated and reliable generic health status instrument developed by the EuroQoL Group. It consists of the EQ-5D descriptive system and a visual analogue scale (VAS), the EuroQoL visual analogue scale (EQ-VAS).

The EQ-5D descriptive system measures a patient's health state on 5 dimensions: mobility, self-care, usual activities, pain/discomfort, and anxiety/depression. The patient is asked to indicate his/her health state by rating each dimension on a five-level scale (1=no problem, 5=extreme problem). This rating resulted in a 5-digit number describing the respondent's health state. It should be noted that the numerals 1-5 have no arithmetic properties and should not be used as a cardinal score.

The EQ-5D Index scores are country specific and range generally from 0 to 1, with 0 representing the worst health state and 1 as perfect health. The index values, presented in country specific value sets, are a major feature of the EQ-5D instrument, facilitating the calculation of quality-adjusted life years (QALYs) that are used to inform economic evaluations of health care interventions.

The EuroQoL visual analogue scale (EQ VAS) records the respondent's self-rated health on a 20-cm vertical, visual analogue scale from 0 (worst imaginable health state) to 100 (best imaginable health state). This information could then be used as a quantitative measure of health as judged by the individual respondents.

### **PGIS**

PGIS and PGIC are employed as anchors for defining a "responder threshold" for MDASI-AML/MDS item Fatigue. PGIS is generally the preferred anchor over PGIC because PGIC may be subject to recall bias. As recommended by the FDA, for this protocol, both anchor scales will be used to provide an accumulation of evidence to help interpret a clinically meaningful score change in MDASI-AML/MDS.

The PGIS is a single-item questionnaire designed to assess patient's overall impression of disease severity at a given point in time. It uses a 4-point Likert scale as follows: In the last 24 hours, my leukemia symptoms are: 1-"Absent (no symptoms)", 2-"mild", 3-"moderate", 4-"severe".

It will be used as an anchor for defining a "responder threshold", on MDASI-AML/MDS and can also be used to create severity categorization for this PRO to enhance interpretation.

## **PGIC**

PGIC is a single-item questionnaire designed to assess the patient’s overall sense of whether there has been a change since starting treatment as rated on a 7 point Likert scale anchored by (1) “very much improved” to (7) “very much worse”, with (4)-“no change”. The PGIC is a measure of “participant rating of global improvement and satisfaction with treatment”.

This instrument is used to determine global improvement as assessed by the patient and as an anchor to define a responder definition for MDASI-AML/MDS and as a sensitivity analysis for defining a “clinical important difference” on this PRO.

### **3.2.4. Other Endpoints**

- PK of glasdegib;
- QTc interval.

CCI [REDACTED]

[REDACTED]

[REDACTED]

[REDACTED]

[REDACTED]

[REDACTED]

[REDACTED]

**C**  
**C**  
**I**

### 3.4. Baseline Variables

The date of first dose (start date) of study treatment is the earliest date of non-zero dosing of any study drug. The date of last dose of study treatment is the latest date of non-zero dosing of any study drug.

No windowing will be applied when defining baseline. Any deviations from the protocol specified window will be documented as protocol deviations.

For efficacy endpoints (except Fatigue) and baseline characteristics the last non-missing assessment prior to randomization will serve as the baseline assessment. For fatigue, similar to other PRO endpoints, the last non-missing measurement on the day of the first dose of study treatment will serve as baseline (note that PRO endpoints are collected prior to study drug dosing on the same day).

For safety (including Eastern Cooperative Oncology Group (ECOG) performance status) the last non-missing assessment performed on or prior to date of the first dose of study treatment (or prior to randomization for patients randomized but not dosed) will serve as the baseline assessment. If there are no observations meeting these criteria, then baseline is considered missing.

For PRO, the measurement, the day of the first dose of study treatment will be used as the baseline measurement. If there are no observations meeting this criteria, then baseline is considered missing.

Triplicate ECGs are collected; therefore the baseline for each ECG measurement is the average of the pre-dose measurements on the baseline day. Unscheduled assessments will not be included in the calculation of the average. The average of the replicate measurements will be determined after the derivation of the individual parameters at each timepoint.

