24. **PRO surveys (MDASI-AML/MDS, EQ 5D 5L, PGIC, PGIS, CCI [REDACTED] refer to Section 7.4):** The surveys will be completed by the patient as described in the Schedule of Activities for Induction, Consolidation, and Follow-up (footnotes 30, 31). Interviewer administration may be used under special circumstances (eg, subject is visually impaired, forgot their glasses, feels too ill). PROs are collected every 7 days up to 28 days during Induction. There is no PGIC on Day 1 of Induction 1 but it will be administered for Day 1 of Induction 2. See footnote #32 for schedule during HSCT consolidation. CCI [REDACTED]. Each PRO will continue to be completed at each Post Treatment Follow Up visit and during the Long-Term Follow-up phase by phone. PROs should never be completed more than once on any calendar day. For subjects hospitalized or with a timepoint falling on weekend or holiday, the PRO may be performed on the next business day. If Consolidation(s) are extended PRO will not continue beyond Day 28.
25. **Blood Samples for glasdegib PK:** See detailed information in Table 2 for specific time points.

CCI [REDACTED]

CCI [REDACTED]

CCI

29. **End of Treatment:** Obtain these assessments if not completed in the last week (last 3 months for BM assessments, unless the patient is coming off study treatment for disease progression). Occurs within 14 days of last dose but may be longer only if dosing was interrupted due to an AE and it led to permanent discontinuation. Subjects continuing to experience toxicity following discontinuation of treatment will be followed at least every 4 weeks by the investigator until resolution or determination, in the clinical judgment of the investigator, that no further improvement is expected.

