#### 7.4. Patient Reported Outcomes (PROs)

Patient reported outcomes will be assessed using the MD Anderson Symptom Inventory AML/MDS Module (MDASI-AML/MDS), EuroQol 5-Dimension questionnaire 5-Level version (EQ-5D-5L), Patient Global Impression of Symptoms (PGIS), and Patient Global Impression of Change (PGIC). CCI [REDACTED]

PROs are completed at the same interval as drug dosing, clinical visits, and post-treatment follow-up are conducted. Refer to [Table 1](#) and [Table 3](#) for specific timepoint requirements. PGIC is completed at all post baseline time points, without the initial baseline assessment. PRO responses will be obtained directly from patients while on treatment and during the first two years of post-treatment follow-up. During the long term follow up phase, PRO responses may be transcribed and entered by site staff. PROs should never be completed more than once on any calendar day. For subjects hospitalized or with a timepoint falling on a weekend or holiday, the PRO may be performed on the next business day.

Site staff role must be strictly limited to transcription and data entry of patient responses, without any attempt to interpret, lead, or influence. Interviewer administration may be used under special circumstances (eg, patient is visually impaired, forgot their glasses, or feels too ill). If interviewer administration is required, every effort should be made to have the same interviewer administer the PRO surveys to the patient. In addition, the interviewer will stay true to the patient's response and not alter it.

Patients must complete these PRO surveys prior to any discussion of the patient's health or treatment with their physician or other healthcare personnel at the site. While every effort should be made to have patients complete these PRO surveys prior to dosing with any study drugs and other clinical procedures, flexibility is allowed to accommodate for site-specific operating procedures.

The data entered into the device will be considered the source documents and sent electronically to the vendor when completed. Patient responses will be captured in a database and maintained by the vendor and transferred to the Pfizer database.

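### The SAP takes the Fatigue baseline only from the first-dose day, but the protocol lets some patients defer the Day 1 questionnaire; those who do have no baseline, and the SAP does not say how they enter the Fatigue test

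*SAP*

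**What the plan says.** SAP Section 3.4 sets the baseline for Fatigue as follows: "the last non-missing measurement on the day of the first dose of study treatment will serve as baseline". For PROs in general it says: "For PRO, the measurement, the day of the first dose of study treatment will be used as the baseline measurement". It adds "No windowing will be applied when defining baseline" and, where no same-day form exists, "If there are no observations meeting this criteria, then baseline is considered missing". The reason it gives is a premise about data collection: "note that PRO endpoints are collected prior to study drug dosing on the same day".

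Protocol Section 7.4, which covers both studies, says: "For subjects hospitalized or with a timepoint falling on a weekend or holiday, the PRO may be performed on the next business day". Table 1 footnote 24, for the intensive study, repeats this: "For subjects hospitalized or with a timepoint falling on weekend or holiday, the PRO may be performed on the next business day". Neither place exempts the baseline visit. Section 7.4 asks sites to try to obtain PROs before dosing, but then says that "flexibility is allowed to accommodate for site-specific operating procedures". Protocol Section 6.2 makes pre-dose collection the default for Day 1 assessments, unless documented otherwise.

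No PRO is scheduled at screening in Table 1 or Table 3, so Day 1 is the only planned baseline.

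**The concern.** The baseline rule is strict because it relies on same-day, pre-dose collection, which the protocol makes the default but does not guarantee. The Document History places the hospitalized, weekend and holiday allowance in Amendment 5. The SAP says that it is based on Amendment 5, yet it keeps the same-day premise. The two texts appear not to have been reconciled.

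Fatigue is the key secondary endpoint and the only one placed after OS in the testing hierarchy (SAP Sections 5.1.2 and 6.2.1). A responder is defined by change from baseline at Week 8 (intensive) or Week 12 (non-intensive). The threshold comes from a model of change in Fatigue on SGIC-S, which is itself a change from baseline PGIS. A missing Day 1 form therefore removes a patient from both steps. The rule for counting that patient in the test is also left open, and that choice affects the result.

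**Working it through.** **Step 1: follow one patient through both documents.** Take a hospitalized patient who receives the first dose on a Friday and completes the first PRO on the following Monday.

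- Protocol Section 7.4 permits this. Section 6.2 discourages it but leaves room for documented exceptions.
- SAP Section 3.4 accepts only the Friday date, so the Fatigue and PGIS baselines are both missing.
- SAP Section 5.2.6 uses unscheduled assessments when deriving PRO baselines, but this does not clearly override the date rule in Section 3.4.
- The plus or minus 3 day window in SAP Section 6.2.1 belongs to the post-baseline weeks. The next-available rule in the same section covers a missing Week 8 or Week 12 form. Neither supplies a baseline.
- SAP Section 5.3 imputes nothing unless otherwise specified.

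The patient therefore has no change in Fatigue, no SGIC-S value and no baseline covariate for the MDASI and EQ-5D mixed models (SAP Sections 6.2.6.1 and 6.2.6.2).

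**Step 2: how the CMH test would count this patient.**

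- *Exclusion:* SAP Section 5.3 says data are evaluated as observed.
- *Retention, in effect as a non-responder:* PRO endpoints use all randomized patients (SAP Section 4.1, Protocol Section 9.3.2). SAP Section 5.2.9 keeps missing observations in the denominator. Its visit-specific rule would also count a patient who has a Week 8 form.

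Section 6.2.1 does not choose between these readings.

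**Step 3: size, under stated assumptions.** The plan gives no sample size, power, responder rate or deferral rate for Fatigue, so there is no figure to reproduce.

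From the documents: 400 intensive and 320 non-intensive patients, randomized 1:1, and a one-sided test.

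Assumed: one-sided level 0.025; true responder rates of 30% and 45%; equal deferral *d* in both arms; no other missing data; no stratification.

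Power = Φ[(Δ − 1.96·SE0)/SE1], where Δ is the difference in rates, SE0 = √[2·p̄(1−p̄)/n] and SE1 = √[(p0(1−p0) + p1(1−p1))/n], with n per arm and p̄ the mean rate.

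Intensive study with no loss (n = 200): SE0 = √(2 × 0.375 × 0.625/200) = 0.0484. SE1 = √((0.21 + 0.2475)/200) = 0.0478. (0.15 − 1.96 × 0.0484)/0.0478 = 1.15, so power is 0.875.

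If deferring patients are excluded, n becomes 200(1−d). If they are kept as non-responders, both rates are multiplied by (1−d): to 28.5% and 42.75% at 5%, and to 27.0% and 40.5% at 10%.

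| Study | Deferral | Patients without baseline | Power, excluded | Power, non-responders |
|---|---|---|---|---|
| Intensive | 0% | 0 | 0.875 | 0.875 |
| Intensive | 5% | 20 | 0.858 | 0.848 |
| Intensive | 10% | 40 | 0.839 | 0.817 |
| Intensive | 28.6% | about 114 | 0.748 | 0.678 |
| Non-intensive | 0% | 0 | 0.794 | 0.794 |
| Non-intensive | 5% | 16 | 0.773 | 0.761 |
| Non-intensive | 10% | 32 | 0.751 | 0.726 |

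The 28.6% row is a stress case: 2/7, as if starts were spread evenly over the week and every weekend starter deferred. Hospitalized weekday starters who also deferred could push it higher. Nothing in the documents makes it likely.

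**The case against.** The strongest reply is that the SAP's rule is sound. A form filled in after days of chemotherapy is not a baseline, and calling it missing avoids a contaminated change score. This stands: the fault lies in the mismatch between the documents, and widening the window forward would make matters worse.

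Second, Protocol Section 6.2 makes pre-dose Day 1 collection the default, and the deferral wording is permissive. This also stands in part. It narrows the gap, but the exception for documented cases keeps it open.

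Third, a form completed after dosing on the same day still meets SAP Section 3.4, so the flexibility on dosing order creates no missing baseline. That is right. Such a form raises only a lesser question of contamination, softened by the MDASI's 24-hour recall.

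A reader might infer that every hospitalized or weekend-start patient loses the key secondary endpoint. The documents do not support this. Only patients who actually defer past the first-dose date are affected, and removal from the test is one of two possible readings. A reader might also infer that the loss falls mainly on the intensive study. That is plausible, but the documents give no rate of hospitalization on Day 1 or of deferral in either study. Nor do they suggest that deferral would differ between blinded arms.

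**Conclusion.** SAP Section 3.4 and Protocol Section 7.4 conflict for the Day 1 PRO. Following both as written leaves any patient who defers it past the first-dose date without a Fatigue or PGIS baseline. That patient cannot be classed as a responder and contributes nothing to the threshold model or to the baseline-adjusted mixed models. Whether the patient is excluded from the CMH test or counted as a non-responder is undefined.

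The frequency cannot be derived from the documents. At an assumed 5 to 10% deferral the loss of power is modest, about 2 to 6 percentage points in the intensive study, and part of that spread comes from the handling the SAP leaves open. These figures rest on assumed responder rates, equal deferral in both arms and no other missing data. The OS analysis is not touched, and Fatigue is tested only if OS is met. This should be corrected because the endpoint is formally tested and the correction is small.

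**What to change.** **Protocol Section 7.4 and Table 1 footnote 24:** state that the next-business-day allowance does not apply to the baseline PRO, and that this PRO may be completed in a short window before first dose, for example up to 3 days. Table 3 footnote 22 has no deferral sentence, so for the non-intensive study the edit belongs in Section 7.4. The window needs its own wording. The 3-day allowance for Day 1 laboratory tests is counted back from randomization, not from first dose.

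**SAP Section 3.4:** define the PRO baseline as the last completed PRO before the first dose of any study drug, judged by time stamp. Use a same-day post-dose form only if there is no earlier one, and flag it. Do not extend the window to later days.

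**SAP Section 6.2.1:** state whether a patient with no baseline is excluded from the CMH test or counted as a non-responder, and report the other handling as a sensitivity analysis.

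**Cost:** no added questionnaire. Some baselines will be up to 3 days old, and the protocol wording must go through an amendment. The Section 6.2.1 statement needs no amendment and is worth making even if the protocol stays as it is.

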#### 3.4.1. Stratification

Randomization is stratified by the following factors:

##### **Intensive Chemotherapy Study:**

- genetic risk (favorable vs intermediate vs adverse by ELN genetic risk categories) and age ( $\leq 60$  years vs  $> 60$  years).

##### **Non-Intensive Chemotherapy Study:**

- genetic risk (favorable vs intermediate vs adverse by ELN genetic risk categories) and age ( $< 75$  years vs  $\geq 75$  years).

The primary analysis will utilize strata as defined in the IVRS system. In addition, sensitivity analysis may be conducted with baseline age and ELN genetic risk category collected in the CRF.

### 3.5. Safety Endpoints

Safety endpoints will be summarized based on the on-treatment period unless otherwise specified.

On-treatment is defined as the time from the first dose of study treatment to last dose prior to HSCT + 28 days and if applicable, from first dose post-HSCT to last dose + 28 days or start of new anti-cancer drug therapy (minus 1 day), whichever occurs first. Note that conditioning regimens for HSCT (regardless of whether glasdegib is resumed after HSCT) are not considered “new anti-cancer drug therapy”. Adverse events occurring on the same day as the first dose of study treatment will be considered to have occurred during the on-treatment period. All other assessments which occur on the same day as the first dose of study treatment will be considered baseline assessments (see [Section 3.4](#) for the definition of baseline).

Safety data collected outside the on-treatment period as described above will be listed but not summarized.

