37. **Interrupt glasdegib/placebo at least 28 days prior to day of hematopoietic stem cell infusion (HSCT).** Following HSCT, subjects may continue glasdegib or matching placebo 30-60 days post first day of HSCT, once there is ANC engraftment, no  $\geq$ Grade 2 ongoing GVHD, and no ongoing SAEs that prevent resuming glasdegib or placebo, in the judgement of the investigator.

CCI

**Table 2. Pharmacokinetics & ECG Schedule for Patients Receiving Intensive Chemotherapy: Glasdegib/Placebo + Daunorubicin/Cytarabine**

Assessment	Screening	Induction 1, and Induction 2  Day 1			Induction 1 and Induction 2  Day 10 (±1 day)			Consolidation  Cycles 1-4, Day 1			Consolidation  Cycles 1-4, Day 10 (±1 day)			Glasdegib following chemotherapy Cycle ≥1, Day 1	End of Treatment
		0 	1	4	0 	1	4	0 	1	4	0 	1	4		
Hour post-dose														1	
Glasdegib/placebo PK Plasma Samples			X	X	X	X	X	X	X	X					
Triplicate 12-lead ECG 	X	X	X	X	X	X	X	X	X	X	X	X	X	X	X

**Abbreviations:** ECG: electrocardiogram; PK: pharmacokinetics.

- Induction Phase:** Glasdegib/placebo PK samples to be collected ONLY in Induction 1.
- Consolidation Phase:** Glasdegib/placebo PK samples to be collected ONLY in Cycles 1 and 2.
- Glasdegib/Placebo PK sample collection:** In all instances, “0 hour” represents a pre-dose collection. The PK sample should be collected within 30 minutes prior to dose administration. Patients should be reminded not to take their study drug prior to arriving at the clinic on protocol scheduled visits. All PK time points are in reference to dosing of glasdegib/placebo. There is a 10% window around the nominal timepoints (1 hour timepoint has a ±6 minute window and the 4 hour timepoint has a ±24 minute window).
- Triplicate 12-lead ECGs (local):** At each time point, 3 consecutive supine 12-lead ECGs will be performed approximately 2 minutes apart to determine mean QTc interval. When matched with PK samples, ECGs will be collected: prior to blood sample collection, such that the blood sample is collected at the nominal planned time. All ECG time points are in reference to dosing of glasdegib/placebo. ECGs will be locally read. A 15-min window for each ECG collection is allowed around the nominal ECG time point.

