#### **9.5.4.1. Summary and Categorical Analysis of Electrocardiogram Findings**

The analysis of ECG results will be based on subjects with both baseline and on-treatment ECG data. All ECGs obtained during the study will be evaluated for safety. ECG collected prior to the first day of dosing will be considered the baseline ECG.

ECG measurements (an average of the triplicate measurements) will be used for the statistical analysis and all data presentations. Any data obtained from ECGs repeated for safety reasons after the nominal time-points will not be averaged along with the preceding triplicates. Interval measurements from repeated ECGs will be included in the outlier analysis as individual values obtained at unscheduled time points.

Data will be summarized and listed for QT, HR, RR, PR, QRS, QTcF and QTcB. Individual QTc (all evaluated corrections) intervals will be listed by time. The most appropriate correction factor will be selected and used for the following analyses of central tendency and outliers and used for the study conclusions.

Descriptive statistics (n, mean, median, standard deviation, minimum, and maximum) will be used to summarize the absolute QTc value and changes from baseline in QTc after treatment, and by treatment and time point. For each subject by treatment the maximum change from baseline will be calculated as well as the maximum post-baseline value across time-points. Outlier analysis of the QTc data will be conducted and summarized as follows:

- The number of subjects with maximum change from baseline in QTc (<30, 30-<60, and  $\geq$ 60 msec);
- The number of subjects with maximum post-dose (post-baseline) QTc ( $\leq$ 450, >450- $\leq$ 480, >480-  $\leq$ 500, and >500 msec);
- PR changes from baseline  $\geq$ 25% and absolute values >200 msec;
- QRS changes from baseline  $\geq$ 25% and absolute values >110 msec;
- Number and percentage of individuals with abnormal ECG findings.

Shift tables will be provided for baseline versus worst on study QTc (one or more correction method will be used). Tables of ECG abnormality at baseline (yes, no, not done: (n, %)) will also be provided. Subjects experiencing clinically-relevant morphological ECG changes will be summarized (including frequency and percentage).

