#### **6.6.5. Electrocardiogram**

Triplicate ECGs assessments are required at each specified nominal visit and time-point as specified in the Schedule of Activities in the Protocol (Table 2 for Intensive and Table 4 for Non-intensive). A mean value is calculated for any replicate measurements having the same nominal visit. The mean measurement is reported.

QTcF and QTcB (both Fridericia and Bazett's correction) will be programmatically derived using the following formula:

$$QTcF(\text{msec}) = QT(\text{msec}) / (60 / \text{HR}[\text{bpm}])^{1/3}$$

$$QTcB(\text{msec}) = QT(\text{msec}) / (60 / \text{HR}[\text{bpm}])^{1/2}$$

QT, RR, HR, PR, QRS, QTcF, and QTcB will be summarized using simple descriptive statistics (mean, standard deviation, median, quartiles, minimum, and maximum) of actual values and change from baseline for each nominal visit over time (ie, unscheduled assessments will be excluded). The total number of patients for change from baseline will include all patients in the treatment arm who have both a baseline and a value at the nominal visit. Baseline will be selected as defined in [Section 3.4](#).

The mean absolute value will be presented with two-sided 95% confidence intervals and the baseline adjusted mean QT, RR, HR, PR, QRS, QTcF and QTcB will be presented with two-sided 90% confidence intervals.

Additionally QTcF and QTcB will be summarized by maximum post-baseline values using the following categories.

- $\leq 450$  msec;
- $>450$  msec but  $\leq 480$  msec;
- $>480$  msec but  $\leq 500$  msec;
- $>500$  msec.

Unscheduled assessments will be utilized in addition to planned assessments.

And maximum increases from baseline in QTcF and QTcB (including scheduled and unscheduled assessments) will be also summarized based on the following categories:

- Change  $\geq 60$  msec;
- Change  $\geq 30$  msec but  $<60$  msec;
- Change  $<30$  msec.

In the event that neither Fridericia's nor Bazett's correction adequately adjusts for heart rate, an additional correction such as a population or patient-specific baseline correction could be used and should be fully justified.

For PR and QRS maximum increases from baseline, the following categories will be applied:

- PR changes from baseline  $\geq 25\%$  and absolute values  $>200$  msec;
- QRS changes from baseline  $\geq 25\%$  and absolute values  $>110$  msec.

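### The SAP's date-based rule for the first dosing day conflicts with its ECG-specific rules and leaves the status of the Day 1 post-dose ECGs open in the QTc tables

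*SAP*

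**What the plan says.** Four places bear on which ECGs are baseline and which are post-baseline.

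- **SAP 3.5 (Safety Endpoints).** "On-treatment is defined as the time from the first dose of study treatment to last dose prior to HSCT + 28 days". Adverse events on the day of first dose are on-treatment. For everything else on that day: "All other assessments which occur on the same day as the first dose of study treatment will be considered baseline assessments", with a pointer to SAP 3.4 for the definition of baseline. The section also says: "Safety data collected outside the on-treatment period as described above will be listed but not summarized".
- **SAP 3.4 (Baseline Variables).** The general safety baseline goes by date: "the last non-missing assessment performed on or prior to date of the first dose of study treatment". ECGs have their own rule: "the baseline for each ECG measurement is the average of the pre-dose measurements on the baseline day".
- **SAP 6.6.5 (Electrocardiogram).** It takes its visits and time points from Protocol Tables 2 and 4 and its baseline from SAP 3.4. The categorical analysis reads: "Additionally QTcF and QTcB will be summarized by maximum post-baseline values using the following categories". Maximum increases from baseline and a baseline-versus-worst shift table follow.
- **Protocol 9.5.4.1.** "ECG collected prior to the first day of dosing will be considered the baseline ECG". The same section limits the ECG analysis to subjects with both baseline and on-treatment ECGs, and in its outlier analysis treats post-dose and post-baseline as the same thing.

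The schedule in Protocol Tables 2 and 4 puts triplicate ECGs on Day 1 at 0, 1 and 4 hours. The Table 2 footnote fixes the clock: "All ECG time points are in reference to dosing of glasdegib/placebo".

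**The concern.** A rule that assigns a whole calendar day to baseline does little harm where Day 1 assessments are taken before dosing, which Protocol 6.2 makes the default. It fails for assessments deliberately scheduled after the first dose on that day, and the 1 h and 4 h ECGs are exactly that.

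Treatment effect on QTc is a stated secondary objective. Protocol 5.8.1 reports Grade 3 QTcF prolongation at the highest doses of the first-in-subject study (400 and 600 mg), and Protocol 1.2.4.1 puts the time of peak glasdegib concentration at 1–4 hours, so the two readings sit in the window where an acute effect would be looked for. If they are classed as baseline, they cannot contribute to a maximum post-baseline value. A patient who dies before Day 10 (intensive) or Day 15 (non-intensive) with no later ECG would then have no post-baseline ECG and could leave the analysis under the Protocol 9.5.4.1 condition. Two programmers working from the same SAP could produce different QTc tables.

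**Working it through.** The plan states no figure to reproduce here. The check compares the rules and counts scheduled time points.

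**Step 1: how each rule treats the Day 1 ECGs**

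| Rule | Day 1, 0 h | Day 1, 1 h and 4 h |
|---|---|---|
| SAP 3.5, same-day sentence read literally | baseline | classed as baseline |
| SAP 3.5, on-treatment definition | before first dose | inside the on-treatment period |
| SAP 3.4, ECG rule | forms the baseline value | not in the baseline value |
| SAP 6.6.5 | baseline as in SAP 3.4 | listed among the Table 2 and 4 time points |
| Protocol 9.5.4.1 | not baseline (same day as dosing) | post-dose, hence post-baseline |

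SAP 3.5 points to SAP 3.4, but SAP 3.4 only says which readings make up the baseline value. It does not say that the other Day 1 readings are post-baseline. The pointer therefore keeps the 1 h and 4 h readings out of the baseline average without settling whether they enter the post-baseline tables.

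**Step 2: how many scheduled readings are affected**

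Inputs: ECG time points in Protocol Tables 2 and 4. The denominator leaves out screening and the Day 1 pre-dose ECG and includes End of Treatment (EOT). It does not count ECGs in single-agent glasdegib/placebo cycles after chemotherapy, which would only lower the percentages. Share lost = 2 / (scheduled time points after the first dose).

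Intensive study. Induction 1 gives 2 (Day 1: 1, 4 h) + 3 (Day 10: 0, 1, 4 h) = 5. Induction 2 and each consolidation cycle give 3 + 3 = 6.

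- Induction 1 + EOT: 5 + 1 = 6; 2/6 = 33%.
- Induction 1 + four consolidation cycles + EOT: 5 + 4×6 + 1 = 30; 2/30 = 7%.
- Both inductions + four consolidation cycles + EOT: 5 + 6 + 4×6 + 1 = 36; 2/36 = 6%.

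Non-intensive study. Cycle 1 gives 2 (Day 1) + 3 (Day 15) = 5; Cycles 2 and 3 give 3 each; Cycle 4 onward gives 1 each.

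- Cycle 1 + EOT: 5 + 1 = 6; 2/6 = 33%.
- Through Cycle 3 + EOT: 5 + 2×3 + 1 = 12; 2/12 = 17%.
- Through Cycle 6 + EOT: 5 + 2×3 + 3×1 + 1 = 15; 2/15 = 13%.

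If SAP 3.4 and 6.6.5 are taken to govern, the loss is 0 in every row. The Day 10 and Day 15 ECGs at 0, 1 and 4 h stay in under either reading.

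**Step 3: direction**

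For a fixed baseline, the maximum over a subset of readings is never larger than the maximum over all of them. Dropping the two readings therefore leaves each patient's maximum QTc and maximum increase equal or lower, and the number of patients in the highest categories equal or lower. The documents hold no data from which to estimate by how much.

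**The case against.** The strongest reply is that the ECG text already shows the intended handling. The on-treatment period opens at the first dose, so 1 h and 4 h fall inside it, and only data outside that period are kept out of the summaries. SAP 3.5 allows for exceptions specified elsewhere, and SAP 6.6.5 is specific: it uses the Table 2 and 4 time points, takes baseline from SAP 3.4, and discusses replicate ECGs at post-dose nominal times. If the specific rule prevails over the general one, nothing is lost. This stands as the better guess at intent. It does not remove the conflict, because the same-day sentence in SAP 3.5 follows the on-treatment definition, names adverse events as its only exception, and is never overridden for ECGs.

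The practical effect is also small for most patients. Steady state is usually reached by Day 8 (Protocol 1.2.4.1), so the retained Day 10 and Day 15 readings reflect higher exposure and are more likely to hold a patient's maximum. Patients who stop early should have an End of Treatment ECG, and unscheduled ECGs enter the maximum tables. The thorough QT study described in the protocol showed no large effect. All of this stands. It confines the consequence mainly to early deaths with no later ECG.

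Protocol 8.4.1 requires mean QTcF prolongation above Grade 2 to be reported as a serious adverse event, so the worst Day 1 values would surface elsewhere. That is a partial safeguard: readings of 481–500 msec, Grade 2 in Protocol Table 10, are outside it.

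Finally, Protocol section 9 lets the SAP modify the protocol's analysis, with an amendment needed only for major changes to the primary endpoint definitions or analyses. The different ECG baseline in Protocol 9.5.4.1 is therefore permissible, but the SAP does not say that it is replacing it.

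**Conclusion.** The point holds as an inconsistency that should be corrected. The same-day rule in SAP 3.5 does not fit the ECG rules in SAP 3.4 and 6.6.5 or in Protocol 9.5.4.1, and the protocol and SAP also define the ECG baseline differently.

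A reader might infer two stronger things. One is that post-dose ECGs contaminate the baseline value; the documents do not support this, because SAP 3.4 restricts the ECG baseline to pre-dose readings. The other is that the plan definitely discards the Day 1 post-dose ECGs; this is also unsupported, because the on-treatment definition, SAP 6.6.5 and Protocol 9.5.4.1 all point toward keeping them. Nor are the Day 1 readings in general the only post-dose ECGs for patients who stop early, since an End of Treatment ECG is scheduled.

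The size depends on the reading chosen: no loss if the ECG-specific text governs, and 33% falling to 6% of scheduled time points after the first dose if SAP 3.5 is applied literally. These shares assume that all scheduled ECGs, including End of Treatment, are done. They describe readings, not patients reclassified, which cannot be estimated from the documents. The effect is limited to descriptive QTc safety summaries.

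**What to change.** Three text changes in the SAP:

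1. In SAP 3.5, limit the same-day sentence to assessments taken before the first dose, or exempt ECGs with a nominal post-dose time.
2. In SAP 3.5 or 6.6.5, state that the Day 1 ECGs at 1 h and 4 h are on-treatment and enter the maximum post-baseline, change-from-baseline and shift summaries.
3. In SAP 3.4, state that its ECG baseline replaces the wording of Protocol 9.5.4.1.

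The cost is a few sentences. The nominal times are already in the schedule, so no new data are needed, and under Protocol section 9 this change does not by itself require a protocol amendment. It should be made before the ECG tables are programmed.
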